## 4. ENDPOINTS

### 4.1 PRIMARY EFFICACY ENDPOINT

The primary efficacy endpoint is:

- ABR (spontaneous and total) during Part 2 when on final MarzAA dose level versus recorded historical ABR

Bleeding events will be evaluated as follows:

- Spontaneous versus traumatic/traumatic

A spontaneous bleeding episode is defined as one that is precipitated by normal ADL.

### 4.2 SECONDARY ENDPOINTS

The secondary endpoints will include:

- Occurrence of breakthrough bleeds requiring escalation to higher dose level.
- Safety parameters: Occurrence of clinical thrombotic event not attributable to another cause, and occurrence of antibody formation resulting in a decreased endogenous level of FVII or FVIIa.
- Change in coagulation parameters (prothrombin time (PT), activated partial thromboplastin time (aPTT), fibrinogen, MarzAA antigen and activity levels, and thrombin generation test (TGT)) from pre-dose.
- Occurrence of an antibody response to MarzAA and whether it is inhibitory and cross-reactive to wt-rFVIIa or wt-FVII.
- Clinically significant levels of thrombogenicity markers resulting from daily SC administration of MarzAA
- Feasibility and ease of use of daily SC self-administration by patient as measured by compliance with treatment
- Breakthrough bleeding events will be categorized as follows:
  - Number of bleeds that are life threatening
  - Number that require hospitalization and/or blood transfusion
  - Number of muscle bleeds

**Statistical Analysis Plan**

Catalyst Biosciences, Inc. **Protocol # MAA-201**

**Version 2.0**

**Syneos Health #1009647**

### **4.3 EXPLORATORY ENDPOINTS**

- Identification of biomarker(s) such as antigen levels, activity levels, or global thrombosis assay evaluation that can be used to predict or correlate with a subject's lack of spontaneous bleeding.
- Identification of biomarker(s) such as D-dimer, F1+2, or a functional assay of the FVIIa activity that will identify or predict clinical thrombogenicity with the daily SC administration of MarZAA.
- Identification of biomarker(s) such as D-dimer, F1+2, or a functional assay of the FVIIa activity that will identify or predict clinical thrombogenicity of daily SC administration of MarZAA when use of rescue medication is required.
- Patient-reported outcome (PRO) measures: European Quality of Life-5 Dimensions (EQ-5D), Visual analogue scale (VAS); Hemophilia A quality of life questionnaire (Haem-A-QoL); Hemophilia Activities List (HAL)

Statistical Analysis Plan

Catalyst Biosciences, Inc. Protocol # MAA-201

Version 2.0

Syneos Health #1009647

## 5. ANALYSIS SETS

### 5.1 SCREENED/ENROLLED SUBJECTS

- Screened Subject: Any subject who signed the study-specific informed consent
- Screen Failures: Any subject who signed the study-specific informed consent but failed to meet study requirements (inclusion/exclusion criteria) during screening
- Enrolled Subject: Any subject who was successfully screened

### 5.2 SAFETY POPULATION

Safety population is defined as any patient who receives at least one dose.

### 5.3 INTENT-TO-TREAT (ITT) POPULATION

ITT population is defined as any patient who receives at least one dose.

### 5.4 MODIFIED ITT POPULATION

Modified ITT population is defined as any patient who receives at least 7 SC doses at 30 µg/kg.

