6.1.2.1 Guidelines for Dose Escalation

An escalation to the next dose level is required if a spontaneous bleeding event occurs after the fifth daily dose on a dose level. A dose escalation will not occur if the subject is on the maximum dose level of 120 µg/kg. A spontaneous bleeding episode is defined as one that is precipitated by normal activities of daily living (ADL). Subjects will use their current bypass regimen for any spontaneous or traumatic bleed that occurs while on study drug.

Three dose escalations are allowed during Part 2: 60, 90, and 120 µg/kg (maximum dose).

Safety parameters and PK/PD assessments at each dose level will be monitored to ensure that dose escalation to a higher dose level is appropriate.

The spontaneous bleeding episode must be reported to the clinical team immediately and determination of a dose escalation will be made on review of available clinical information related to the spontaneous bleeding episode and may require subsequent treatment and laboratory data, including available results from the PK/PD/safety assessments.

A decision to proceed with dose escalation will be made by the principal investigator in agreement with personnel who have Sponsor, or designee, medical oversight responsibility.

If there is disagreement amongst any of those individuals, the decision will be reviewed on an urgent basis by an independent Medical Consultant for Safety Oversight.

MAA-201 VERSION 2.0

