8.2.5.2 Day 50 Visit

The following procedures will be performed:

- Medical and Hemophilia History (including that obtained from review of diary entries of bleeding episodes and treatment, AEs, and PRO scales)
- Concomitant medications
- Vital signs
- Diary entry of PRO scales (see **Appendix B** – EQ-5D, VAS; Haem-A-QoL; HAL)
- Physical examination
- Clinical signs of thrombosis (see **Appendix A**)
- Hematology and chemistry (see Footnote 3 for **Table 1** in **Section 1.3, Schedule of Activities**)
- Coagulation assays: PT, aPTT, fibrinogen, FVII, FVIIa activity, and TGT
- Thrombogenicity markers: D-dimer, F1+2, and TAT
- PK: MarzAA antigen and activity
- IP compliance and proficiency confirmation
- Study drug dispensing, inventory and accountability
- Adverse events

8.2.6 Part 2 – If Spontaneous Bleeding Occurs after the fifth daily dose (Duration: ≥ 50 Days)

If a spontaneous bleeding episode occurs in Part 2 after the fifth daily dose, necessitating a dose escalation, the “day count” will be reset to zero. The day a spontaneous bleeding event occurs (and subsequent days until the event is resolved) is considered Day 0. Dose escalation starts on the next day (Day 1).

MAA-201 VERSION 2.0

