9.3 POPULATIONS FOR ANALYSES

Safety population: any patient who receives at least one dose

Efficacy/PD ITT population: any patient who receives at least one dose

Efficacy/PD modified ITT population: any patient who receives at least 7 SC doses at 30 µg/kg

Efficacy/PD per protocol population: any patient who completes at least 50 exposure days (SC product)

If a subject does not complete the study as defined in the protocol (i.e., before receiving study drug for 50 days at the same dose level) another subject will need to be enrolled in replacement.

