**Part 1: Single dose administration**

**Part 1a (24 hours):** Single IV administration of MarzAA at 18 µg /kg with assessment of PK, PD, and safety for 24 hours post-dose.

**Part 1b (48 hours):** Single SC administration of MarzAA at 30 µg /kg with assessment of PK, PD, and safety for 48 hours post-dose

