#### Part 2: Daily SC administration

At Day 1 of daily SC dosing, subjects will begin their self-administered dosing regimen. MarzAA will be self-administered by subjects daily (at approximately the same time every day), starting with a SC dose of 30 µg/kg MarzAA. At each dose, subjects will record the day and time of the SC injections in their diary. If a spontaneous bleeding episode (defined as one that is precipitated by normal activities of daily living [ADL]) occurs before the fifth daily dose, subjects will continue at the current dosing level. If a spontaneous bleeding episode occurs after the fifth daily dose, the MarzAA dose will be escalated to the next dose level. Three dose escalations are allowed during part 2: 60, 90, and 120 µg/kg (maximum dose). At each dose level escalation, safety and PK/PD will be monitored to ensure that dose escalation to a higher dose level is appropriate. If a subject requires a third dose escalation to the fourth dose level, then they will continue treatment with that dose for 50 days and complete the study, regardless if a spontaneous bleeding episode occurs during the highest treatment dose level.

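### Modified ITT counts only doses at 30 µg/kg, so a spontaneous bleed just after the fifth daily dose can keep a subject out of it

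*SAP*

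**What the plan says.** SAP 5.4 defines modified ITT as "any patient who receives at least 7 SC doses at 30 µg/kg", and Protocol 9.3 has the same rule: "Efficacy/PD modified ITT population: any patient who receives at least 7 SC doses at 30 µg/kg". Doses at 60, 90 or 120 µg/kg do not count.

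Protocol 6.1.2.1 sets the escalation trigger: "An escalation to the next dose level is required if a spontaneous bleeding event occurs after the fifth daily dose on a dose level". Under Protocol 8.2.6 the higher dose begins the day after the bleed has resolved. For an earlier bleed, SAP 3.6 says that if it "occurs before the fifth daily dose, subjects will continue at the current dosing level".

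Part 1b has already given each subject a "Single SC administration of MarzAA at 30 µg /kg" (SAP 3.3). Neither definition says whether that dose is one of the seven.

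The primary test uses ITT (SAP 8.1.1). Modified ITT is one of two sensitivity populations for it (SAP 8.1.2). It is also used for breakthrough bleeds, between-bleed intervals and proportion of bleeding days (SAP 8.2.1), and for thrombotic events (SAP 8.2.2). Per-protocol asks for 50 exposure days at the highest dose level (SAP 5.5).

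**The concern.** A minimum-exposure rule should remove subjects who had too little drug to be informative. This one can remove a subject who had plenty of drug, because he bled at a particular time and was escalated. Membership then depends on a post-baseline efficacy outcome.

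Such a subject could go on to complete 50 days at 60 µg/kg. He would then be in ITT and in per-protocol but not in modified ITT. A per-protocol set that is not contained in modified ITT suggests that the dose restriction was not checked against the escalation rule.

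The stake is largest in the SAP 8.2.1 analyses. There the bleed that excludes the subject is itself an outcome at 30 µg/kg. It drops out of the modified ITT results together with everything he contributes at higher doses. His escalated-dose exposure also leaves the modified ITT summary of thrombotic events.

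**Working it through.** The plan gives no figure for how many subjects modified ITT will lose, so there is none to reproduce.

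**Step 1: count the doses.** Assume one injection a day in Part 2, none missed, and no further 30 µg/kg dose once the bleed has occurred.

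| Spontaneous bleed falls | 30 µg/kg SC doses, Part 2 only | With the Part 1b dose | In modified ITT? |
|---|---|---|---|
| before daily dose 5 | dosing continues at 30 µg/kg | same | not excluded by this bleed |
| after dose 5, before dose 6 | 5 | 6 | no, on either reading |
| after dose 6, before dose 7 | 6 | 7 | only if Part 1b counts |
| after dose 7 | 7 | 8 | yes, on either reading |

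The exclusion window is 1 dosing day if the Part 1b dose counts and 2 if it does not. The conflict remains on the reading kinder to the plan, because 6 is less than 7.

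**Step 2: chance of a bleed in the window.** Inputs are N = 12 (SAP 3.5) and the plan's two rates, 12 (null) and 6 (alternative), used here as assumed spontaneous rates per year. With a constant rate and a window of d days:

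p = 1 − exp(−rate × d / 365.25)

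expected exclusions = 12p

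chance of at least one = 1 − (1 − p)^12

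For example, rate 12 and d = 1 give p = 1 − exp(−0.03285) = 0.0323.

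| Assumed rate | Window | p per subject | Expected among 12 | At least one of 12 |
|---|---|---|---|---|
| 12 | 1 day | 3.2% | 0.39 | 33% |
| 12 | 2 days | 6.4% | 0.76 | 55% |
| 6 | 1 day | 1.6% | 0.20 | 18% |
| 6 | 2 days | 3.2% | 0.39 | 33% |

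Each exclusion removes 1/12, or about 8%, of the planned sample. At each rate these are upper bounds, because the last assumption in Step 1 need not hold.

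**Step 3: effect of the change.** If doses at any level counted, a subject who escalates after dose 5 or 6 and stays on treatment would reach seven. Exclusions caused by escalation alone would be zero.

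**The case against.** A reader might infer that the rule drops early failures and so tilts the primary-endpoint sensitivity analysis in the drug's favour. The documents do not support that. The sensitivity analysis repeats the ABR at the final dose. The triggering bleed happened at 30 µg/kg, so for an escalated subject it is not counted in any population. Under Protocol 4.2, completing at 60 or 90 µg/kg requires 50 days without spontaneous bleeding. Dropping such a completer removes a stretch free of spontaneous bleeds and could raise the pooled rate, against the drug. Only a subject who ends at 120 µg/kg could complete with spontaneous bleeds at his final dose.

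A simulation with assumed gamma variation between subjects (mean rate 12, squared coefficient of variation 0.25 to 1.0) gives excluded subjects a mean underlying rate of about 15 to 24, against 11.3 to 11.9 for those kept. That concerns underlying rates, not the final-dose ABR, so it does not settle the direction.

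A reader might also infer that early bleeders in general are excluded, or that exclusion is certain after a bleed in the window. Neither follows. Bleeds before the fifth dose leave the subject at 30 µg/kg. Protocol 6.1.2.3 makes interruption during a bleed optional, and Protocol 4.1 leaves continued dosing to the study team after discussion with the sponsor. A subject who keeps injecting 30 µg/kg until the bleed resolves may reach seven.

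Three further points stand. SAP 8.1.1 treats 12 as the total of spontaneous and traumatic bleeds, while inclusion criterion 2 ties it to spontaneous bleeding; only spontaneous bleeds trigger escalation. At a rate of 6 there is a 67% to 82% chance that nobody is lost. And because results are reported for all three populations, a one-subject difference would be visible.

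None of this removes the conflict between the two rules. It limits its size and the claim about direction.

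**Conclusion.** The defect is real but small. As written, modified ITT can exclude a subject because of a spontaneous bleed in a window of one or two dosing days, even if he completes treatment and qualifies for per-protocol. The chance that this happens to at least one of 12 is at most 33% to 55% at an assumed spontaneous rate of 12 per year and 18% to 33% at 6. These figures assume a constant rate, independent subjects, daily dosing and no 30 µg/kg dose after the bleed.

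The primary ITT test is untouched, and the effect on the final-dose ABR sensitivity analysis has no established direction. The firmer consequence is for the by-dose-level bleed analyses in SAP 8.2.1, whose modified ITT versions lose the triggering bleed and all of that subject's later data. Whether the Part 1b dose counts is a separate gap in the definition.

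**What to change.** Define modified ITT as at least 7 SC doses of MarzAA in Part 2, at any dose level. This keeps a minimum-exposure requirement and stops escalation by itself from excluding anyone who stays on treatment. It also settles that the Part 1b dose does not count, which fits SAP 12.1, where exposure is calculated for Part 2 only. No dose, schedule or escalation rule changes.

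Make the change in SAP 5.4, list it in SAP Section 14 as a departure from the protocol, and align Protocol 9.3 at the next amendment, since Protocol 10.1.10 sends protocol changes to the IRB/IEC.

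The cost is a minor documentation change and no new data. One limitation remains: the set still conditions on post-baseline exposure, so a subject who bleeds and stops treatment before his seventh Part 2 dose stays out.

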### 5.5 PER PROTOCOL POPULATION

Per protocol population is defined as any patient who completes at least 50 exposure days at the highest dose level(SC product). Any protocol deviations which will have impact on the primary endpoint will be determined before database lock, based on a review of all protocol deviations.

### 5.6 PHARMACOKINETIC (PK) POPULATION

PK population is defined as any patient who has received one dose and has at least one measured PK concentration post-dose. The PK data will be listed for this population and used in all PK analyses. The PK data for subjects with protocol deviations affecting the results may be excluded from summaries and analyses. Any Protocol deviations pertaining to the validity of PK analyses (and thus inclusion in the PK population) will be determined before the database lock (and receipt of PK data), based on a review of all protocol deviations.

### 5.7 PHARMACODYNAMIC (PD) POPULATION

PD population is defined as any patient who has received one dose and who has PD data pre-dose or post-dose. The PD data will be listed for this population and used in all PD and PK/PD analyses. The PD data for subjects with protocol deviations affecting the

**Statistical Analysis Plan**

Catalyst Biosciences, Inc. **Protocol # MAA-201**

**Version 2.0**

**Syneos Health #1009647**

results may be excluded from summaries and analyses. This will be determined before the database lock based on review of all protocol deviations.

## **5.8 PROTOCOL DEVIATIONS**

Protocol deviations will be listed. All major protocol deviations will be summarized in the study report for the following deviation category:

- Inclusion criteria
- Exclusion criteria
- Treatment deviation (incorrect or missed doses)
- Improper informed consent procedure
- Noncompliance (SAE not reported)
- Visit schedule (out of window)
- Procedure not per protocol, or visit not done
- Concomitant medication
- Laboratory sample (not done or results not available)
- Other

Statistical Analysis Plan

Catalyst Biosciences, Inc. Protocol # MAA-201

Version 2.0

Syneos Health #1009647

## 6. GENERAL ASPECTS FOR STATISTICAL ANALYSIS

### 6.1 KEY DEFINITIONS

#### 6.1.1 Baseline

Baseline is defined as the last assessment (pre-dose) prior to the first administration of the study drug in Part 1a. This baseline will be used for both part 1a and part 1b, and will be used in all efficacy and safety analyses in [section 12](#)

For the baselines for PK and PD analyses, they will be defined separately in [Section 9](#) and [Section 10](#).

### 6.2 MISSING DATA

Missing data will not be imputed in this study. All analyses will be based on available data.

### 6.3 VISIT WINDOWS

All data will be organised and analysed according to the scheduled visits outlined in the protocol. However, if the scheduled visit is not available in the dataset, unscheduled visit will be mapped to a scheduled visit for analysis using the date and/or time of collection/assessment to mapped to the intended visit using the visit window specified below. If more than one record occurs within the same visit window where only one assessment is expected, then the following rule should be applied: for pre-study assessments the last non-missing result prior to study drug administration should be used; for post-treatment assessments the closest non-missing result to the scheduled visit should be used.

Study Part	Visit in Protocol	Analyses Visit	Visit Window
Part 1a	Hr 0	Part 1a, Hr 0	-
	5 min	Part 1a, 5 min	3 - 7 min
	30 min	Part 1a, 30 min	28 - 32 min
	Hr 1	Part 1a, Hr 1	50 - 70 min
	Hr 3	Part 1a, Hr 3	170 - 190 min
	Hr 6	Part 1a, Hr 6	350 - 370 min
	Hr 9	Part 1a, Hr 9	510 - 570 min
	Hr 12	Part 1a, Hr 12	690 - 750 min
	Hr 24	Part 1a, Hr 24	1350 - 1530 min
Part 1b	Hr 3	Part 1b, Hr 27	1610 - 1630 min
	Hr 5	Part 1b, Hr 29	1730 - 1750 min
	Hr 7	Part 1b, Hr 31	1850 - 1870 min
	Hr 9	Part 1b, Hr 33	1950 - 2010 min

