Study Treatment and Assessments:

Part 1a: Single IV administration

Each subject will receive an IV dose of 18 µg/kg MarZAA. PK, PD, and safety assessments will be collected pre-dose and post-dose at 5 and 30 minutes and at Hour 1, 3, 6, 9, 12, and 24.

Part 1b: Single SC administration

After the initial 24 hours, the same subject will receive a SC dose of 30 µg/kg MarZAA. PK, PD, and safety assessments will be done at pre-dose and repeated at Hour 3, 5, 7, 9, 12, 24, 30, and 48. At any time during this period, subjects will be trained by appropriate study staff to self-administer a SC injection.

Part 2: Daily SC administration

At Day 1 of daily SC dosing, subjects will begin their self-administered dosing regimen. MarZAA will be self-administered by subjects daily (at approximately the same time every day), starting with a SC dose of 30 µg/kg MarZAA. At each dose, subjects will record the day and time of the SC injections in their diary. If a spontaneous bleeding episode (defined as one that is precipitated by normal activities of daily living [ADL]) occurs before the fifth daily dose, subjects will continue at the current dosing level. If a spontaneous bleeding episode occurs after the fifth daily dose, the MarZAA dose will be escalated to the next dose level. Three dose escalations are allowed during part 2: 60, 90, and 120 µg/kg (maximum dose). At each dose level escalation, safety and PK/PD will be monitored to ensure that dose escalation to a higher dose level is appropriate. If a subject requires a third dose escalation to the fourth dose level, then they will continue treatment with that dose for 50 days and complete the study, regardless if a spontaneous bleeding episode occurs during the highest treatment dose level.

Treatment of a spontaneous bleeding episode: Subjects will use their current bypass regimen for any spontaneous or traumatic bleed that occurs while on study drug. If treatment for a breakthrough bleeding episode is needed, then subjects will contact the clinical investigative team immediately to report the event; treatment dose administered; and determine follow-up plans for that event, including to arrange for a blood specimen to be drawn (if feasible) before further administration of either study drug or bypassing agent used for treatment. This information will also be recorded in the subjects' diary.

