	Day 0*	Day 7 (+1d)	Day 14 (± 2d)	Day 21 (± 2d)	Day 28 (± 2d)	Day 42 (± 3d)	Day 50 (+3d)	Un- scheduled ¹⁰	End of Study ¹¹	
Medical and Hemophilia History ¹	X	X	X	X	X	X	X	X	X	
Concomitant Medications	X	X	X	X	X	X	X	X	X	
Vital Signs	X	X	X	X	X	X	X	X	X	
Weight	X	X	X	X	X	X	X	X	X	
Physical Examination	X	X	X	X	X	X	X	X	X	
Clinical Signs of Thrombosis ²	X	X	X	X	X	X	X	X	X	
Hematology and Chemistry ³		X	X	X	X	X	X	X	X	
Coagulation Assays ^{4,6}	X ⁵	X	X	X	X	X	X	X	X	
Thrombogenicity markers ^{4,6}		X	X	X	X	X	X	X	X	
Pharmacokinetic (PK) sampling ^{4,6}	X ⁵	X	X	X	X	X	X	X	X	
Immunogenicity assays ^{4,7}	X ⁵		X		X	X ⁷		X ⁷	X	
Troponin level ³	X	X						X		
Diary entry of PRO scales ⁸		X	X	X	X	X	X	X	X	
Diary entry of IP, bleeding episodes and treatment, AEs, injection site assessment	X	X	X	X	X	X	X	X	X	
Adverse Events	X	X	X	X	X	X	X	X	X	
SC Daily MarzAA administration ⁹		←								
IP compliance & proficiency confirmation		X	X	X	X	X	X	X	X	
IP dispensing, inventory and accountability	X	X	X	X	X	X	X	X	X	

*** NOTE:** When a spontaneous bleeding episode and dose escalation occurs, the "day count" is reset to zero. The day the spontaneous bleeding episode occurs and subsequent time until treatment resolution is considered Day 0. Dose escalation starts the next day (Day 1).

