8.2.4 Part 2 (Duration: \geq 50 Days)

Please refer to **Section 1.3, Schedule of Activities (SOA)** and specifically Table 3 and 4 for the sequence of events that should occur during the Part 2 process.

MAA-201 VERSION 2.0

Part 2 procedures will be the same for all subjects; there are modifications in the schedule of follow-up visits and assays drawn for those subjects who have no spontaneous bleeding occurrence after the fifth daily dose, as shown in **Section 1.3, Schedule of Activities** and specifically **Table 3** and for those who have an interim spontaneous bleeding event requiring dose escalation as shown in **Section 1.3, Schedule of Activities** and specifically **Table 4**.

Day 1 of Part 2 will start the next morning right after Part 1b is completed. During Part 2, subjects will self-administer MarzAA SC daily in the morning at 30 µg/kg. Subjects will record daily in their diary: the injection day/time, dose, spontaneous or traumatic bleeding episodes that may occur and whether bypassing treatment is administered, which agent, and what dose, AEs that may occur, and injection site assessment.

Subjects will return to the clinic the day after Part 1b for the Part 2, Day 1 assessments.

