### 9.3 PRESENTATION OF CONCENTRATION DATA

#### 9.3.1 Handling of missing data

Missing concentration and activity data for all subjects who are administered scheduled study treatments will be considered as non-informative missing and will not be imputed. No concentration estimates will be provided for missing sample values.

For the derivation of PK parameters, the following rules will apply:

Concentration values below the assay's lower limit of quantification (BLQ) in pre-dose samples and in samples taken before the time of the first quantifiable concentration will be treated as zero;

The sampling time of pre-dose samples relative to dosing will also be treated as zero;

Post-dose BLQ values after the first quantifiable time point will be set to missing.

If the actual time of sampling is missing, the planned time may be used.

Samples taken outside the sampling windows may be excluded from by-time point summary statistics; this will be determined prior to database lock.

For PK concentration and activity summary, individual concentration versus time curves and mean concentration versus time graphs, the following rules will apply:

PK concentrations BLQ in pre-dose samples and in samples taken before the time of the first quantifiable value will be set to zero;

The PK concentrations BLQ after quantifiable concentration will be set to zero.

No further imputation will be applied to any missing values.

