## 9.5 DOSE PROPORTIONALITY FOR MARZAA

Analysis of dose proportionality in Part 2 will be performed by a repeated measures ANOVA model using the SAS Proc Mixed procedure if sufficient number of data points for different dose levels for SC injection route only are available. The analysis will be performed using the loge-transformed, dose-normalized, Cmax/D and Cmin/D as dependent variable, visit (Days 7, 14, 21, 28, and 50 relative to start of dosing for dose level 1 or day of dose escalation) and treatment as fixed effect. VisitVisit will be specified as repeated measurement. Subject as random effect.

The comparison will be performed for at least 2 dose levels with at least 6 subjects of PK data available (Cmin or Cmax values for each time point). Pair-wise comparisons will be made between test dose levels of 60, 90 and 120 µg/kg and the reference dose group of 30 µg/kg.

95% CIs for the geometric mean ratios (GMRs) will be obtained from the mixed-effects model. The formula for the calculation of the estimated ratio between the test and reference and the (1-2\*α)\*100 % CI of the ratio is given below.

- Difference = Estimate of difference between test and reference LSMs

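### SAP 6.3 counts the windows for mapping unscheduled records from the first IV dose, so the mapping fails after a late SC dose and, on virtually every allowed day, after a dose escalation

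*SAP*

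**What the plan says.** SAP 6.3 opens with a default: "All data will be organised and analysed according to the scheduled visits outlined in the protocol". The window table is a fallback. If a scheduled visit is not in the dataset, an "unscheduled visit will be mapped to a scheduled visit for analysis using the date and/or time of collection/assessment". The section does not state the time origin of the table.

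The protocol sets the clocks differently:

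- **SC dose in Part 1b.** Protocol 1.1: "After the initial 24 hours, the same subject will receive a SC dose of" 30 µg/kg. No latest time is given. Protocol Table 1 allows ±1.5 h on the Part 1a Hr 24 assessments. Protocol Table 2 counts its sampling times from its own dosing hour.
- **Start of Part 2.** Protocol 8.2.4: "Day 1 of Part 2 will start the next morning right after Part 1b is completed".
- **Escalation.** Protocol 6.1.2.1: "An escalation to the next dose level is required if a spontaneous bleeding event occurs after the fifth daily dose on a dose level". The note to Protocol Table 4, repeated in SAP 3.8, begins "When a spontaneous bleeding episode and dose escalation occurs, the" and goes on to set the day count back to zero. Day 0 lasts until the bleed has resolved, and the new dose level starts on Day 1.

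Elsewhere the SAP follows the reset. Section 9.5 takes visits "relative to start of dosing for dose level 1 or day of dose escalation". Sections 9.3.3 (PK), 10.3.3 (PD) and 11.3 (immunogenicity) likewise count post-escalation time from the escalation.

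**The concern.** A mapping table works only if its clock starts where the protocol's visit clock starts. In Part 1b that is the SC dose, and in Part 2 it is Day 1 of the current dose level. The 6.3 table uses neither. Escalation is built into the design and Part 2 can run to 197 days (Protocol 4.2), yet the table has no Day 0 row, no post-escalation rows and nothing beyond day 56.

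At stake is the labelling of replacement records. The laboratory and vital-sign summaries (SAP 12.4, 12.5) and the PRO summaries (SAP 8.3.1 to 8.3.4) are by dose level and visit, and no re-anchoring is stated for them. With 12 subjects, one record placed at the wrong visit, or at none, is visible in a by-visit summary. For PK, PD and immunogenicity, the programmer is left with two conflicting clocks.

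**Working it through.** **1. Reproduce the printed table.** Inputs are the nominal times and tolerances in Protocol Tables 1 to 3.

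- Part 1a: nominal ± tolerance. Hr 24: 1440 ± 90 = 1350–1530 min, as printed.
- Part 1b: 1440 + nominal ± tolerance. Hr 3: 1440 + 180 ± 10 = 1610–1630 min. Hr 48: 1440 + 2880 ± 90 = 4230–4410 min. Both as printed.
- Part 2: nominal day + 3, with the protocol tolerance. Day 50 (+3): 53–56 days, as printed.

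All 24 timed rows reproduce from an IV-dose origin. None of the 8 Part 1b rows reproduces from an SC-dose origin. The SAP's own labels agree: Part 1b Hr 3 is relabelled Hr 27, and Part 2 Day 3 is relabelled Day 6.

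**2. Late SC dose.** Let the SC dose be given *d* min later than 24 h after the IV dose, with the replacement record drawn exactly on time after the SC dose. Its time on the 6.3 clock is 1440 + *d* + nominal, so it leaves its own window once *d* exceeds the tolerance.

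| Delay *d* | Hr 3, 5, 7 (±10) | Hr 9, 12 (±30) | Hr 24, 30, 48 (±90) |
|---|---|---|---|
| 10 min | correct | correct | correct |
| 15 or 30 min | no window | correct | correct |
| 60 min | no window | no window | correct |
| 90 min | Hr 3, 5 no window; Hr 7 labelled Hr 9 | no window | correct |
| 120 min | labelled Hr 5, 7, 9 | no window | no window |

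At 90 min, the Hr 7 record falls at 1440 + 90 + 420 = 1950 min, the lower bound of the Hr 9 window. At shorter delays the failure is a missing label, not a wrong one.

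**3. Escalation.** Let *D* be the Part 2 day on which Day 0 falls and *v* the visit day at the new dose level. On the 6.3 clock the study day is 3 + *D* + *v*.

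- *D* = 20, Day 7: 3 + 20 + 7 = 30, inside 29–33, so it is labelled Day 28.
- *D* = 20, Day 21: 3 + 20 + 21 = 44, inside 42–48, so it is labelled Day 42.
- *D* = 6: Days 7, 14 and 21 fall on 16, 23 and 30 and are labelled Days 14, 21 and 28. Days 28, 42 and 50 fall on 37, 51 and 59 and match nothing.

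Now take *D* from 5 to 50 (46 values; the trigger is a bleed after the fifth daily dose) and the six Table 4 visits, assuming one escalation and a bleed resolved the same day. The Table 4 tolerances allow 2 + 5 + 5 + 5 + 7 + 4 = 28 visit days, and 46 × 28 = 1,288.

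| Grid | Correct | Wrong label | No label |
|---|---|---|---|
| Nominal days, *D* = 6 to 50 (45 × 6 = 270) | 0 | 75 | 195 |
| Nominal days, *D* = 5 to 50 (46 × 6 = 276) | 0 | 78 | 198 |
| All allowed days, *D* = 5 to 50 (1,288) | 3 | 313 | 972 |

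The 3 correct cases are Day 42 visits done 2 or 3 days early with *D* = 5 (study days 48 and 47), or 3 days early with *D* = 6 (study day 48).

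**4. Sensitivity.** If Part 2 starts on study Day 5, a literal reading of Protocol 8.2.4, 1 of 1,288 is correct. A longer bleed or a second escalation moves the visits further along the 6.3 clock.

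**The case against.** The strongest reply is scope. SAP 6.3 keeps scheduled records at their protocol visit, so a scheduled Hr 3 sample after a late SC dose stays Hr 3, and a scheduled Day 7 visit after escalation stays Day 7. This stands. The grids in the working are illustrations of the mapping rule and do not count records at risk.

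A reader might also infer that valid absorption-phase samples would be dropped from the PK summaries, because SAP 9.3.1 says "Samples taken outside the sampling windows may be excluded from by-time point summary statistics". The documents do not support that. The sentence is permissive and does not refer to the 6.3 table. The protocol has its own sampling tolerances, counted from the SC dose, and a late SC dose does not breach them.

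The ±1.5 h belongs to the Hr 24 assessments and not to the SC dose, and the title of Protocol Table 2 places Part 1b directly after Part 1a. Long delays may therefore be uncommon. Even so, no latest time is set for the SC dose, and just over 10 min is enough to lose the Hr 3, 5 and 7 windows.

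Finally, the Part 2 rows include Days 3 and 5, which exist only at the first dose level, so the table may be meant for that level alone. On that reading post-escalation windows are missing rather than wrong. SAP 6.3 does not say so, and the remedy is the same. Reporting by dose level does keep a mislabelled record within its own dose level, but the visit is still wrong.

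**Conclusion.** The point holds, as a minor defect in a fallback rule. The 6.3 windows are counted from the IV dose. A replacement Part 1b record loses its window once the SC delay exceeds its tolerance: above 10 min for Hr 3, 5 and 7, and above 30 min for Hr 9 and 12. After an escalation, a replacement record gets a wrong label or none on 1,285 of 1,288 allowed combinations (313 + 972). This conflicts with the reset in the protocol and with the PK, PD and immunogenicity sections of the SAP, and it mainly touches the by-visit laboratory, vital-sign and PRO summaries.

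The result assumes that the printed table is applied at every dose level, that Part 2 starts on study Day 4 as the table implies, that there is one escalation, and that the bleed resolves the same day. How many records will need mapping cannot be known from the documents. It would be wrong to infer that the primary result is at risk: the ABR uses bleed counts and exposure days (SAP 8.1.1), not these windows.

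**What to change.** In SAP 6.3, state the time origin and re-base the table, keeping the protocol tolerances:

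- **Part 1b:** minutes from the actual SC dose, for example Hr 3 = 170–190 and Hr 48 = 2790–2970.
- **Part 2:** days from Day 1 of the current dose level: Day 7 = 7–8, Day 14 = 12–16, Day 21 = 19–23, Day 28 = 26–30, Day 42 = 39–45, Day 50 = 50–53. Keep Days 3 and 5 (3–4 and 5–6) for the first dose level only.
- **After escalation:** use the Table 4 visits and add a Day 0 row running from the bleed to its resolution.

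With these origins, no SC delay moves an on-time record out of its window, and all 1,288 enumerated combinations map correctly. It would also help to say in SAP 9.3.1 that its sampling windows are the protocol tolerances and not the 6.3 table.

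The cost is one revised SAP table and a sentence or two. Neither the protocol nor data collection changes.
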